4.1.4 Last on-treatment

The last on-treatment value is defined as the last measurements taken within 1 day (2 days, on QOD regimen) after last ZS dose (scheduled or unscheduled). For by-visit summary, the last on-treatment measurement during the respective phase will be additionally displayed.

4.1.5 Handling of drop outs and missing data

4.1.5.1 Missing central lab individual measurements of S-K

In the event of missing S-K data from the central laboratory, the i-STAT data will be used to replace missing data by adjusting for the average paired difference between the central and i-STAT levels collected at the same visit. As illustration of the change methodology, if the mean difference between central laboratory and i-STAT assessments for all patients with both values available at the relevant visit is 0.12 mmol/L higher for the central laboratory assessment, then 0.12 mmol/L will be added to the i-STAT level to impute the missing central laboratory assessment.

The above imputation procedure for missing central lab S-K based on non-missing i-STAT level will be carried out separately for samples tested on or before 3rd-December-2017 and for samples tested on or after 4th-December-2017.

If both central lab S-K and i-STAT are missing, the measurement at that visit/timepoint will be left as missing.

4.1.5.2 Handling of early study discontinuation

For subjects who discontinue the study medication before completion, the last assessment will be mapped according to the algorithm outlined in section 4.1.3.

4.1.6 Descriptive summary of continuous variables

Descriptive summary of continuous variables includes n, mean, standard deviation (SD), median, minimum and maximum). In the summary of change or percent change from baseline values, 95% confidence interval (95%CI) for the mean (percent) change from baseline will be calculated based on t-distribution.

4.1.7 Descriptive summary of categorical variables

Descriptive summary of categorical variables will consist of frequencies and percentages.

4.1.8 Descriptive summary and analysis of binomial proportions

For proportions of responders (e.g. patients with normokalemia), percentage and its exact (Clopper-Pearson) 95%CI will be provided.

4.1.9 Repeated measures mixed model for log-transformed S-K

A longitudinal repeated measures analysis using direct likelihood will be performed. The SAS procedure PROC MIXED will be used. The dependent variable will be the log-transformed S-K values measured post-baseline during the MP. The least square means (LSMeans) and its 95%CIs for each visit (time point) as well as the average over certain period of time will be derived from the model by specifying appropriate contrasts. The model estimates (LSMeans and 95%CIs) will be back transformed to original scale.

The model will include the fixed categorical effect of Visit and fixed continuous covariate of CP baseline S-K, MP baseline S-K and baseline eGFR. Age category (<55, 55-65, >= 65 years) and binary indicators for presence of Heart Failure, CKD, Diabetes and RAASi use will also be included. An unstructured matrix of within-subject error variance covariance will be used. The denominator degrees of freedom will be calculated according to Kenward-Roger method.

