The number of normokalemic days during the MP will be calculated assuming that the time interval between assessments is normokalemic only if both the beginning and end assessments for that time interval display normal S-K values. If an intermediate scheduled assessment time point is missing, then the scheduled assessment is regarded as not normokalemic. In order to determine this variable all scheduled or unscheduled fasting S-K will be taken into calculation. Descriptive statistics and 95% CI for mean for the number of normokalemic days will be provided.

- Change in S-K level from the last on-treatment Maintenance Phase visit to the End of Study

To investigate if S-K increases after stopping treatment, change in S-K from last on-treatment visit to MP EOS (MP follow up) visit will be summarized with continuous summary statistics and 95% CI for mean.

Sensitivity analysis for missing S-K values

For the mean S-K over time, longitudinal repeated measures model specified above will serve as a sensitivity check to missing S-K values. It provides estimates of S-K over time *had subjects remained on ZS for planned 52 weeks* under the Missing At Random assumption.

Further sensitivity analyses may be conducted depending on the volume of missing data as well as on the reason of study discontinuation.

Sensitivity analysis with iSTAT potassium measurements

Since the ZS dose adjustment during study is based on iSTAT measurement, analyses with categorized values (e.g. proportion of subjects with normokalemia) are expected to be sensitive to which of S-K or iSTAT K are analysed.

Summary of Potassium value over time, proportion of subjects with normokalemia and number of normokalemic days will be repeated using iSTAT potassium measurements instead of S-K values provided by Central lab. Only observed iSTAT values measured within last ZS dose + 1 day (+ 2 days on QOD regimen) will be used.

Sensitivity analysis with iSTAT potassium measurements for Correction Phase will be also carried out as outlined in section 4.2.5

Analysis with S-K adjusted for assay change bias

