Assay for S-K in Covance was updated during the study, on 4th December 2017. A sensitivity analysis will be performed by subtracting the average bias (0.208 mmol/L) between the old and the new assays from all the Central lab S-K measurements analysed by the new assay. Primary analysis will be repeated on this new dataset containing all original S-K measurements analysed by the old assay and the adjusted measurements analysed by the new assay, i.e.

- S-K (adjusted) = S-K (reported) for data measured by old assay
- S-K (adjusted) = S-K (reported) – 0.208 mmol/L for data measured by new assay

By doing this, the adjusted measurements will be on the same "level" as the S-K measurements analysed by the old assay, and results will reflect what could have been observed had the assay not been changed.

Summary of S-K over time as well as proportion of subjects (normokalemia, hyperkalemia, hypokalemia) will be repeated using S-K adjusted for assay change instead of S-K values provided by Central lab.

Subgroup analysis of S-K related variables

The summary of proportions (normokalemia, hyperkalemia, hypokalemia) by visit and mean change from baseline will be provided by the following subgroups :

- By Heart Failure (Yes, No)
- By CKD (Yes, No)
- By DM (Yes, No)
- By Baseline RAASi use (Yes, No)
- By Baseline Diuretics use (Yes, No)
- By Baseline eGFR (<30, 30-<60, >= 60)
- By Baseline S-K (< 5.5, 5.5 -< 6.0, >=6.0 mmol/L)
- By Baseline Weight (<65, >= 65 kg)
- By Age (<65, >= 65 years, < 75, >= 75 years)
- By Gender

Analysis of S-Aldosterone and S-Bicarbonate

- Change from baseline in S-Aldosterone over time
- Change from baseline in S-Bicarbonate over time

Observed values at each visit (including last on treatment) and changes from baseline will be summarized by descriptive summary statistics. For change from baseline, 95%CI will be also presented.

- Proportion of patients with normal S-Aldosterone
- Proportion of patients with normal S-Bicarbonate

Number (%) of subjects who can maintain normal S-Aldosterone levels and S-Bicarbonate, respectively, at each Maintenance Phase study visit and last on treatment visit will be tabulated with binomial proportion and its 95%CI. Normal reference ranges provided by Central laboratory vendor will be used for these analyses.

- SF-36 v2 questionnaire

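### The mixed model reports single-arm LSMeans of serum potassium without fixing the covariate margins, and its age classes overlap at 65

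*SAP*

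**What the plan says.** SAP section 4.1.9 specifies a repeated-measures model for post-baseline log S-K in the Maintenance Phase (MP). On software: "The SAS procedure PROC MIXED will be used". On the fixed effects: "The model will include the fixed categorical effect of Visit and fixed continuous covariate of CP baseline S-K, MP baseline S-K and baseline eGFR". It then adds: "Age category (<55, 55-65, >= 65 years) and binary indicators for presence of Heart Failure, CKD, Diabetes and RAASi use will also be included". Visit LSMeans "as well as the average over certain period of time will be derived from the model by specifying appropriate contrasts", and the results are back-transformed. The section does not state the covariate weights behind an LSMean or a period average, nor whether the four indicators are CLASS or numeric variables.

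Section 4.2.4.1 gives the model its purpose: a sensitivity check for missing S-K, estimating S-K over time "had subjects remained on ZS for planned 52 weeks" under missing at random. The same section also reports observed S-K by visit with no covariate weighting.

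On age, the demographic table (section 4.2.2) and the S-K and adverse-event subgroups (sections 4.2.4.1 and 4.2.7.1) use two separate splits, at 65 and at 75. Neither overlaps.

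**The concern.** An LSMean is a model prediction at chosen covariate values. In a two-arm trial with an additive model, the choice drops out of the treatment difference. Section 1.2 describes one arm, so here the LSMean itself is the result and the choice stays in it.

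The standard PROC MIXED definition weights the levels of each CLASS effect equally. A three-level age category would ordinarily be a CLASS effect, so that convention would apply to age however the indicators are coded. Numeric covariates are set at their mean over records. If the dataset holds one record per observed visit, subjects who stay longer then count more, which is an awkward margin for a check on missing data.

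The stake is the reading of that check. It compares the model estimate with the observed means. If the two differ partly because the covariates were reweighted, the gap cannot be attributed to drop-out, and its absence is not reassuring either. The model is the only sensitivity analysis for missing mean S-K that section 4.2.4.1 commits to; the further ones are optional.

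The age classes are a separate drafting error: a subject aged exactly 65 meets two definitions.

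**Working it through.** **Inputs from the SAP.** Single arm (1.2); 150 enrolled, 35% drop-out, target of 100 with one year of data (1.3); Visits 7 to 23 after MP baseline (Table 3); model terms (4.1.9). The SAP gives no figure for the model. Its sample size is reproduced within rounding: 100/0.65 = 154 against 150, and 150 × 0.65 = 97.5 against 100. Nothing below depends on it except the simulation sizes, 98 and 150.

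**Assumptions.** Case mix, factor effects, a residual SD of 0.10 on the log scale, independent factors and a single time point.

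**1. Precision.** For an additive model with independent factors, the SE of an equal-weight LSMean relative to one at observed margins is √(1 + A + B), where

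- A = Σ (1/3)²/p_k − 1 over the three age classes;
- B = Σ (0.5 − p)²/(p(1 − p)) over the four indicators.

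If only age is a CLASS effect, B = 0.

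| Mix | Age <55 / 55–64 / ≥65 (%) | HF, CKD, DM, RAASi (%) | A | B | Ratio, age only | Ratio, all | Simulated, all, n = 150 |
|---|---|---|---|---|---|---|---|
| Balanced | equal thirds | 50, 50, 50, 50 | 0 | 0 | 1.00 | 1.00 | 1.02 |
| Mild | 15/25/60 | 30, 70, 50, 60 | 0.370 | 0.423 | 1.17 | 1.34 | 1.38 |
| Moderate | 10/20/70 | 20, 80, 55, 65 | 0.825 | 1.234 | 1.35 | 1.75 | 1.82 |
| Strong | 5/15/80 | 15, 90, 60, 70 | 2.102 | 2.971 | 1.76 | 2.46 | 2.60 |

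At n = 98 the simulated ratios for the three unbalanced mixes are 1.40, 1.86 and 2.67.

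**2. Shift.** Suppose every factor changes S-K by b on the log scale, all effects push the same way, and both younger classes differ equally from ≥65. Near 4.6 mmol/L the shift is 4.6 × (exp(bD) − 1), with D = Σ|0.5 − p| + |1/3 − p(≥65)|.

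| Mix | D | b = 0.01 | b = 0.02 | b = 0.04 |
|---|---|---|---|---|
| Mild | 0.500 + 0.267 = 0.767 | 0.035 | 0.071 | 0.143 |
| Moderate | 0.800 + 0.367 = 1.167 | 0.054 | 0.109 | 0.220 |
| Strong | 1.050 + 0.467 = 1.517 | 0.070 | 0.142 | 0.288 |

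These are worst cases. With effects of 0 to 2% and mixed signs, the simulated shifts at n = 150 are 4.639 − 4.623 = 0.016, 4.651 − 4.622 = 0.029 and 4.660 − 4.620 = 0.040 mmol/L. With age alone as a CLASS effect and b = 0.01 to 0.02, the formula gives 0.012 (mild, 0.01) to 0.043 (strong, 0.02). Balanced factors or b = 0 give zero.

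**3. Validity of the interval.** Moderate mix, n = 150: the average model SE of the equal-weight LSMean is 0.0149 and its empirical SE is 0.0156. The interval is about right for its own target.

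**4. Record weighting.** Visits 7 to 23 give 17 possible records. A subject who leaves after Visit 9 has 3. In the extreme case where the whole 35% left there, with one record per observed visit, their weight in a numeric covariate's mean would be (0.35 × 3)/(0.35 × 3 + 0.65 × 17) = 1.05/12.10 = 8.7%, not 35%.

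**5. Observed margins.** With complete data, the LSMean at subject-level margins equals the observed mean of log S-K (4.651 and 4.651 after back-transformation, moderate mix). This is a geometric mean. The arithmetic mean would still be higher by about 4.6 × (exp(0.10²/2) − 1) = 0.023 mmol/L at the assumed SD.

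**The case against.** The strongest reply is that the SAP never prescribes equal weighting. It says only that appropriate contrasts will be specified, and a careful programmer could choose observed margins. The four comorbidity and RAASi terms are called binary indicators, which reads naturally as 0/1 numeric variables, and those are not split evenly. This stands. A reader might infer that the plan imposes a population with half of each comorbidity, but the text does not say so. What remains is that the weighting is open, that the standard definition would govern age, and that numeric coding still leaves the record-weighting question.

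Three further inferences also fail:

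- **The overlap at 65 causes the shift or the wide intervals.** It does not. It only leaves the class of subjects aged exactly 65 undefined.
- **The confidence intervals are wrong.** They are valid for a different target and generally less precise.
- **The trial's S-K results as a whole describe the wrong population.** Section 4.2.4.1 also reports observed values, changes, proportions and subject-level averages, none of them covariate-weighted. Section 4.1.1 calls all analyses descriptive, and the primary objective is safety.

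It is also fair to say that model age classes need not match subgroup cut-offs. The mismatch with 65 and 75 used elsewhere is not an error; the overlap is.

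**Conclusion.** The point holds for the model-based S-K estimates. Section 4.1.9 leaves open the margins of a quantity that, in a single arm, depends directly on them. Under the standard definition the result would not describe the FAS-MP subjects whom section 4.2.4.1 has in view, so the missing-data check would be confounded with reweighting.

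Under the assumed mild-to-strong mixes, the SE is about 1.2 times (mild, age only) to 2.5 times (strong, all factors) that at observed margins. A plausible shift is roughly 0.02 to 0.1 mmol/L. It could be larger if effects are strong and all in one direction, and it is zero if the factors are balanced or have no effect. Correlated factors would change these figures. The SAP gives no case mix or coefficients, so they show scale and do not predict the trial's result.

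The overlap at age 65 is certain from the text but small, and independent of the rest.

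**What to change.** State in section 4.1.9 that every visit LSMean and every period-average contrast is evaluated at FAS-MP subject-level margins, each subject counting once. Either route would do:

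- Enter the age terms, indicators and continuous covariates as numeric variables centred at their FAS-MP subject means, and evaluate all LSMeans and contrasts at zero. Centring alone is not enough, because the procedure would average the centred columns over records again.
- Supply an observed-margins (OM) dataset in which every FAS-MP subject is crossed with every visit, and use the same weights in the period contrasts. One record per subject would not carry all levels of Visit, and an LSMEANS option does not by itself set the weights of contrasts written by hand.

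Make the age classes disjoint, for example <55, 55 to <65 and ≥65, or use age as a continuous covariate. When the model estimates are set against observed data, use observed geometric means so that the two are on the same scale.

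The cost is a short paragraph of SAP text and a few lines of code. No data collection changes, and the primary safety analyses and observed S-K summaries stay as they are.

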4.2 Analysis methods

4.2.1 Study patients

4.2.1.1 Disposition of patients

The disposition of subjects for the enrollment period, correction phase treatment period, the maintenance phase treatment period and follow-up period will be summarized.

The summary of disposition for the enrolment period will include all Enrolled subjects (who signed informed consent).

The summary of disposition for correction phase will include SAF-CP. This summary will include subjects completing and discontinuing the correction phase treatment period.

The summary of disposition in the maintenance phase treatment will include SAF-MP. This summary will include subjects completing and discontinuing the maintenance treatment

period up-to Visit 17 (MP Day 194) and up-to Visit 23 (MP Day 362), broken down by reasons for discontinuation.

The summary of disposition in CP follow up period will include all subjects who discontinued correction phase or completed correction phase but did not enter MP. The summary of disposition in MP follow up period will include all subjects who discontinued or completed MP. For each, summary will include subjects completing and discontinuing the follow up period, broken down by reason for discontinuation.

4.2.2 Demographics and baseline characteristics

Demographic and other baseline characteristics, including disease-related characteristics will be summarized, using the SAF-CP as well as SAF-MP.

Demographic and baseline characteristics are listed in [Table 4](#). Disease-related common baseline characteristics are listed in [Table 5](#).

Table 4 Demographics

Characteristics	Summarized as	Categories
Sex	Categorical	Male, Female
Age	Categorical and Continuous	<65, >= 65 years <75, >= 75 years
Body Weight	Categorical and Continuous	< 65, >= 65 kg
BMI	Continuous	
Height	Continuous	
Race	Categorical	Asian, Other

Table 5 Disease-related characteristics

Characteristics	Summarized as	Categories
CP Baseline S-K	Categorical and Continuous	< 5.5 mEq/L, 5.5-< 6.0 mEq/L, >= 6.0 mEq/L
Baseline eGFR*	Categorical and Continuous:	<15 mL/min/1.73m2, 15-<30 mL/min/1.73m2 30-<60 mL/min/1.73m2 >= 60 mL/min/1.73m2
Comorbidity – Heart Failure	Categorical	Yes, No
Comorbidity - Diabetes	Categorical	Yes, No
Comorbidity - CKD	Categorical	Yes, No

Characteristics	Summarized as	Categories
RAAS Inhibitor Use	Categorical	Yes, No
Diuretic Use	Categorical	Yes, No
On peritoneal dialysis	Categorical	Yes, No

*eGFR derived by Japan guideline formula;

$$eGFR[\text{mL}/\text{min}/1.73\text{m}^2] = \text{SCr}[\text{mg}/\text{dL}]^{-1.094} \times \text{Age}[\text{years}]^{-0.287} (\times 0.739 \text{ for female})$$

All summaries of continuous characteristics will be based on non-missing observations. For categorical characteristics, percentages will be calculated out of the total number of subjects in the analysis set (ie, each denominator includes the number of subjects with missing/unknown values for the characteristic).

Comorbidities will be based on medical history (ongoing), using the following search criteria:

- HF will be searched by standardised MedDRA query (SMQ) (narrow) “Cardiac failure”.
- DM will be searched by SMQ (narrow) “Hyperglycaemia/new onset diabetes mellitus”.
- CKD will be searched by SMQ (narrow) “Chronic kidney disease”.

Current medications were based on concomitant medication used at the time of 1st dose of ZS, using the following search criteria :

- Current RAASi use will be searched by anatomical therapeutic chemical (ATC) class ‘C09’ or ‘C03DA’
- Current Diuretic use will be ATC class ‘C03’, ‘C02LG’, ‘C07CB’, ‘C09BA’, or ‘C09DA’

Medical history

The number (%) of subjects with each past and current medical histories as well as surgical history will be summarized by system organ class (SOC) and preferred term (PT) using SAF-CP as well SAF-MP.

4.2.3 Extent of Exposure

4.2.3.1 Study Medication

Correction phase

Duration of exposure (defined as the last CP dose date – first CP dose date + 1), and number of doses taken (at most 9) will be summarized by categorical/continuous descriptive statistics, using SAF-CP.

Maintenance phase

The following summary will be provided using SAF-MP.

The extent of exposure to study medication during the MP (defined as the last MP dose date – first MP dose date + 1) will be summarized with number (%) of subjects with certain duration, where the categorization would be 1-7, 8-30, 31-90, 91-180, 181-270, 271-360, and > 360. The mean (SD), median, and range of the number of days of exposure will also be presented. In addition, total subject-years/days will be calculated using the sum of the exposure to study medication for all subjects.

The extent of exposure to each ZS dose level during the MP will be defined as sum of the dose intervals (end date - start date + 1) during which that dose level is given. The extent of exposure to each ZS dose level will also be summarized using continuous summary statistics and total subject-years/days to each dose level. The summary will be presented also by subjects' maximum dose level.

Following summaries of exposure during MP will be provided to describe the distribution of dose level actually administered in the study:

- number (%) of subjects with at least one dose taken by dose level
- number (%) of subjects by mode dose level (dose level used for longest duration per subject), by maximum dose level, and by last dose level
- Summary statistics of mean daily dose (sum of all administered dose (g) divided by duration of exposure (day)) during entire maintenance phase
Note: the drug interruption period will also be considered as part of duration of exposure (denominator) but will add "0" dose to the numerator.

Further, dose regimen on the target day of scheduled visit will be summarized with proportions of patients treated by each dose regimen on that day to show the general distribution of dose regimen over time. In addition, proportion of subjects with each sequence of dose change will be summarized, if considered meaningful.

4.2.3.2 Prior and concomitant medication

Prior medications are defined as medications taken with a start date that falls before the first dose of study medication (ZS) of Correction Phase.

Concomitant medications include medications that started prior to, but continued after, the first day of a study phase, or medication changes (including newly initiated medications) during a study phase.

All prior medication and concomitant medications will be coded with the WHO Drug Dictionary, and summarised by phase for their respective safety analysis sets.

4.2.3.3 Measurements of Treatment Compliance

Percent treatment compliance is calculated for the maintenance phase. For each type of medication, percent compliance is defined as the sum of ZS doses actually taken divided by the sum of dispensed ZS doses that should have been taken. A subject is considered compliant if percent compliance is $\geq 80\%$ and $\leq 120\%$. In this calculation, period of temporary interruption will also be counted in the period when ZS should have been taken as assigned by IxRS.

4.2.4 Efficacy

4.2.4.1 Efficacy in the Maintenance Phase

Analysis of S-K related variables

- Proportion of patients who can maintain normokalemia (defined as S-K level of ≥ 3.5 and ≤ 5.0 mmol/L, inclusive) on ZS at each Maintenance Phase study visit

Number (%) of subjects who can maintain normokalemia at each Maintenance Phase study visit and last on treatment visit will be tabulated with binomial proportion and its 95%CI.

- Proportions of patients who were hypokalemic (< 3.5 mmol/L) or hyperkalemic (> 5.0 mmol/L) at each Maintenance Phase visit.

For each visit and last on treatment, patients will be classified to either normokalemic, hypokalemic or hyperkalemic by their S-K value. Number and proportion for each category will be tabulated.

- Observed values at visit and change from baseline in S-K over time

Observed S-K values at each visit/last on treatment and changes from CP baseline and from MP baseline will be summarized by descriptive summary statistics. For changes from baseline, 95%CI will be also presented.

- Subject-level average S-K over certain period of time
- Proportion of patients with average S-K ≤ 5.1 mmol/L
- Proportion of patients with average S-K ≤ 5.5 mmol/L

Average S-K level per subject will be calculated over the certain period of time (as specified in section 3.2.1). Continuous summary statistics will be provided for each. In addition, number (%) of subjects meeting ≤ 5.1 or ≤ 5.5 mmol/L will also be summarized with binomial proportion and its 95%CI.

- Model-based estimates for S-K over time as well as average S-K levels over certain period of time

The log-transformed S-K data will be analysed with mixed model as described in section 4.1.9. All post-baseline data will be included into the model. The LS Mean and 95% CI at each timepoint as well as over certain period of time (as specified in section 3.2.1) will be produced using appropriate contrasts. The estimates and 95% CIs will be back-transformed to original scale and tabulated.

- Number of normokalemic days during Maintenance Phase

The number of normokalemic days during the MP will be calculated assuming that the time interval between assessments is normokalemic only if both the beginning and end assessments for that time interval display normal S-K values. If an intermediate scheduled assessment time point is missing, then the scheduled assessment is regarded as not normokalemic. In order to determine this variable all scheduled or unscheduled fasting S-K will be taken into calculation. Descriptive statistics and 95% CI for mean for the number of normokalemic days will be provided.

- Change in S-K level from the last on-treatment Maintenance Phase visit to the End of Study

To investigate if S-K increases after stopping treatment, change in S-K from last on-treatment visit to MP EOS (MP follow up) visit will be summarized with continuous summary statistics and 95% CI for mean.

Sensitivity analysis for missing S-K values

For the mean S-K over time, longitudinal repeated measures model specified above will serve as a sensitivity check to missing S-K values. It provides estimates of S-K over time *had subjects remained on ZS for planned 52 weeks* under the Missing At Random assumption.

Further sensitivity analyses may be conducted depending on the volume of missing data as well as on the reason of study discontinuation.

Sensitivity analysis with iSTAT potassium measurements

Since the ZS dose adjustment during study is based on iSTAT measurement, analyses with categorized values (e.g. proportion of subjects with normokalemia) are expected to be sensitive to which of S-K or iSTAT K are analysed.

Summary of Potassium value over time, proportion of subjects with normokalemia and number of normokalemic days will be repeated using iSTAT potassium measurements instead of S-K values provided by Central lab. Only observed iSTAT values measured within last ZS dose + 1 day (+ 2 days on QOD regimen) will be used.

Sensitivity analysis with iSTAT potassium measurements for Correction Phase will be also carried out as outlined in section 4.2.5

Analysis with S-K adjusted for assay change bias

Assay for S-K in Covance was updated during the study, on 4th December 2017. A sensitivity analysis will be performed by subtracting the average bias (0.208 mmol/L) between the old and the new assays from all the Central lab S-K measurements analysed by the new assay. Primary analysis will be repeated on this new dataset containing all original S-K measurements analysed by the old assay and the adjusted measurements analysed by the new assay, i.e.

- S-K (adjusted) = S-K (reported) for data measured by old assay
- S-K (adjusted) = S-K (reported) – 0.208 mmol/L for data measured by new assay

By doing this, the adjusted measurements will be on the same "level" as the S-K measurements analysed by the old assay, and results will reflect what could have been observed had the assay not been changed.

Summary of S-K over time as well as proportion of subjects (normokalemia, hyperkalemia, hypokalemia) will be repeated using S-K adjusted for assay change instead of S-K values provided by Central lab.

Subgroup analysis of S-K related variables

The summary of proportions (normokalemia, hyperkalemia, hypokalemia) by visit and mean change from baseline will be provided by the following subgroups :

- By Heart Failure (Yes, No)
- By CKD (Yes, No)
- By DM (Yes, No)
- By Baseline RAASi use (Yes, No)
- By Baseline Diuretics use (Yes, No)
- By Baseline eGFR (<30, 30-<60, >= 60)
- By Baseline S-K (< 5.5, 5.5 -< 6.0, >=6.0 mmol/L)
- By Baseline Weight (<65, >= 65 kg)
- By Age (<65, >= 65 years, < 75, >= 75 years)
- By Gender

Analysis of S-Aldosterone and S-Bicarbonate

- Change from baseline in S-Aldosterone over time
- Change from baseline in S-Bicarbonate over time

Observed values at each visit (including last on treatment) and changes from baseline will be summarized by descriptive summary statistics. For change from baseline, 95%CI will be also presented.

- Proportion of patients with normal S-Aldosterone
- Proportion of patients with normal S-Bicarbonate

Number (%) of subjects who can maintain normal S-Aldosterone levels and S-Bicarbonate, respectively, at each Maintenance Phase study visit and last on treatment visit will be tabulated with binomial proportion and its 95%CI. Normal reference ranges provided by Central laboratory vendor will be used for these analyses.

- SF-36 v2 questionnaire

In the CSR, only descriptive summary will be provided. Any further analyses of SF-36 v2 questionnaire will be reported outside the CSR. Note that the scoring for SF-36v2 will be based on standard algorithm using the validated software by OPTUM.

Descriptive summary at baseline and Week 52 will be provided for the following variables

- eight subscale composite scores (Physical Functioning (PF), Role-Physical (RP), Bodily Pain (BP), General Health (GH), Vitality (VT), Social Functioning (SF), Role-Emotional (RE), Mental Health (MH))
- physical component summary (PCS) score and mental component summary (MCS) scores from standard 2-component model

Number (%) of patients with each category will be provided for the following variable :

- Reported Health Transition score (HT) (compared to 1 year ago)

